## 1. Study Summary

Study Title	Shift-and-persist and cardiometabolic markers among women in Puerto Rico: a pilot of a mindfulness-based trial.
Study Design	One arm behavioral intervention
Primary Objective	To evaluate the feasibility and acceptability of a 4-week mindfulness program among young women in Puerto Rico with elevated stress
Secondary Objective(s)	To explore changes in psychological resilience, health behaviors, stress, and cardiometabolic markers
Research Intervention(s)/Interactions	3 study assessments (baseline, post-intervention, 1mo post-intervention)  4-week intervention (1 weekly virtual session)
Study Population	Young women residing in Puerto Rico (18-29y) with elevated stress
Sample Size	30
Study Duration for individual participants	2-4 months
Study Specific Abbreviations/ Definitions	MBSR: mindfulness-based stress reduction
Funding Source (if any)	Emory BIRCWH program

## 2. Objectives

1. To evaluate the feasibility and acceptability of a 4-week mindfulness program among young women in Puerto Rico with elevated stress
2. To explore changes in psychological resilience, psychological distress, health behaviors, and cardiometabolic markers (blood pressure, pulse, weight, and waist circumference).

## 3. Background

Cardiometabolic diseases among women in Puerto Rico. The 1.7 million women residing in Puerto Rico (99% identifying as Latinx) experience a great load of cardiometabolic diseases (i.e., adiposity, type 2 diabetes, hypertension, and hyperlipidemia). It is estimated that, among women in PR, the prevalence of overweight and obesity is 67.1%, hypertension 39.2%, hyperlipidemia 36.8%, and type 2 diabetes 16.3%, with estimates of obesity and type 2 diabetes being higher than in men. With cardiometabolic diseases driving the majority of deaths and disability in Puerto Rico -including women, the steep

**Protocol Title:** Shift-and-persist and cardiometabolic markers among women in Puerto Rico: a pilot of a mindfulness-based trial

---

societal and individual cost of these diseases-particularly in the context of Puerto Rico's financial crisis, it is imperative to understand modifiable factors influencing women's cardiometabolic health and guide early prevention efforts.

Psychological well-being and cardiometabolic health. Psychological well-being has gained attention as a protective factor against cardiovascular disease. This is of particular importance to women in Puerto Rico as they report greater psychological distress than Puerto Rico men. The protective effect of psychological well-being on cardiometabolic health is believed to partially occur by buffering the effects of stress on health. This is of particular importance to women in Puerto Rico given that stress has been shown to be detrimental to Latinx cardiometabolic health. Puerto Ricans in the mainland US have lower psychological well-being, as measured by optimism, than other Latinx heritage groups. Although studies of psychological well-being in Puerto Rico women are scarce, our preliminary work suggests that women on the island also have lower optimism scores than Latinx women on the mainland US (unpublished data). Prioritizing studies on well-being among women in Puerto Rico is of utmost importance given their disproportionate exposure to stressors: a 15 year-long economic crisis, the ravaging 2017 hurricane season (Hurricanes Irma and María) and its subsequent humanitarian crisis, the 2020 sequence of tremors, ongoing political turmoil, and the highest poverty rate in the US, among others.

Mindfulness-based Stress reduction programs (MBSR). The high burden of cardiometabolic diseases among women in Puerto Rico, their disproportionate exposure to stressors, and potentially low psychological well-being, highlight the need for effective behavioral interventions. The American Heart Association has issued a call to action for studies testing mindfulness-based interventions for cardiometabolic health. At its core, this program empowers participants to develop a profound awareness of the present moment, fostering a deeper understanding of their thoughts, emotions, and bodily sensations. Through mindfulness meditation and a series of carefully crafted exercises, MBSR equips individuals with powerful tools to manage stress, reduce anxiety, and enhance their overall well-being. MBSR consists of an 8 week program with weekly sessions (usually lasting 2.5hrs), daily practice exercises (of 45min duration each) and an end-of-program day-long retreat. MBSR has been shown to improve psychological well-being, with studies documenting greater intervention effectiveness and acceptability for women than men. Additionally, studies have shown that mindfulness-based interventions reduce adiposity and hypertension. However, there is limited data on MBSR in Latinx women-less in Puerto Rico. The Puerto Rico population has unique socio-cultural values and norms that merit MBSR to be tested in this group.

MBSR interventions have critical pitfalls, such as time and transportation barriers, that need to be addressed to improve implementation. The only study in Puerto Rico evaluating a MBSR reported time commitment and lack of transportation as barriers to participation. [name] and [name] at UMass Medical School did some preliminary work to address these limitations. They, have adapted the original MBSR to use shortened weekly sessions (1.5- 1hr) and home practice exercises (5-15min). They also selected 4 sessions out of the original 8-week MBSR sessions to shorten the program. This responds to preliminary data from our focus group discussions among young women in Puerto Rico documenting that an 8-week long program with weekly sessions was a burden and would hinder participation.

We took these modifications by [name] and [name] and further made adaptations to make the 4-week MBSR program to be delivered virtually. The original 4-week protocol by [name] and [name] was already

---

available in English and Spanish. In the present study, we will test the feasibility and acceptability of the Spanish version 4-week MBSR program among young women (18-29yr) with elevated stress residing in Puerto Rico, and will explore changes in resilience, stress, health behavior, and cardiometabolic outcomes. Testing the Spanish 4-week MBSR protocol in young women in Puerto Rico is needed to evaluate novel strategies that may be feasible and acceptable for this group.

#### **4. Study Endpoints**

##### **Primary endpoints:**

- Rates of recruitment and retention, adherence, and satisfaction. Adherence will be measured by the number of phone sessions attended and the frequency of self-reported completed home practice, both assessed at post-intervention assessments.
- Ratings of satisfaction, also assessed by survey in post-intervention assessments, will be measured with several questions, including one that reads “Overall, how satisfied were you with the stress reduction program”, “How satisfied are you NOW (after the stress reduction program) with your ability to manage the stress in your life?”, and “¿How much did the program helped you manage your stress?”
- We will also ask questions on satisfaction of the instructor and group setting: “Did you feel that the other participants cared about the group?”, “You felt that the instructor was very knowledgeable about the program”, “It was easy for you to communicate with the instructor”, and “Did you feel that the instructor cared about you?”

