#### **5. Study Intervention/Design**

This is a one-arm intervention study that will explore if a 4-week MBSR program is feasible and acceptable among young women in Puerto Rico with elevated stress. The intervention consists of 4 weekly virtual sessions and daily mindfulness exercises at home (between 5-16min of duration each, according to participant's availability). The participants will also complete three study assessments: baseline, post-intervention, and 1-month post-intervention. All study measures at all time points will be done online through questionnaires to be filled out by participants.

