## **18. Data Analysis, Management and Confidentiality**

Baseline descriptive statistics will include frequencies for categorical variables and means and standard deviations for continuous ones. Recruitment, adherence, retention, and satisfaction will be calculated for the total sample and will be explored by sociodemographic characteristics (i.e., age, income, employment, and education level). Changes in each secondary outcome will be evaluated using mixed

---

linear regression models controlling baseline covariates. We will conduct exploratory analyses among those with high levels of adherence (vs. low). STATA version 17 and SAS version 9.4 will be used.

Sample size considerations are driven by publications regarding pilot study planning. A minimum of 12 individuals per group is recommended for feasibility and precision around the estimates. Other MBCT pilot studies have included a similar sample size. This sample size suits the goals of this study to assess feasibility.

All study staff will be up to date with the Collaborative Institutional Training Initiative (CITI) Human Subjects trainings and will be trained for all protocols, including informed consent and data collection. The research team will maintain all responses and documents confidential. Individuals participating in the intervention will be informed that information disclosed within the intervention sessions is considered confidential and should not be repeated outside of the group. The data collected will only be used for research purposes. Only the research team will have access to the files. The electronic consent form and eligibility criteria will remain stored electronically. Identifiable information will not be shared to anyone and will be kept in a password-protected computer at Emory University and in the PI's OneDrive/SharePoint files.

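### The primary feasibility and acceptability rates have no set criterion, denominator or confidence interval, so the plan can describe them but cannot support a pre-specified conclusion

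*Combined protocol and SAP*

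**What the plan says.** The primary objective (Section 2) is "To evaluate the feasibility and acceptability of a 4-week mindfulness program among young women in Puerto Rico with elevated stress". Section 3 puts it more firmly: "we will test the feasibility and acceptability of the Spanish version 4-week MBSR program". Section 5 puts it more softly: the study "will explore if a 4-week MBSR program is feasible and acceptable".

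Section 4 names the primary endpoints as "Rates of recruitment and retention, adherence, and satisfaction". On adherence it says: "Adherence will be measured by the number of phone sessions attended and the frequency of self-reported completed home practice", both taken at the post-intervention assessment. Satisfaction is also taken there, through several survey questions.

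The schedule table in Section 6 places the number of sessions attended and satisfaction at the post-intervention assessment only. Home-practice frequency appears there and again at one month. Section 5 says that all measures are online questionnaires completed by participants.

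The whole primary analysis is one sentence in Section 18: "Recruitment, adherence, retention, and satisfaction will be calculated for the total sample and will be explored by sociodemographic characteristics". The same section supports the sample size with a rule of thumb of at least 12 per group and concludes: "This sample size suits the goals of this study to assess feasibility".

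**The concern.** Anyone who follows Sections 4 and 18 to the letter will obtain four sets of point estimates. To go from those to a statement that the program is feasible and acceptable, they must decide which women to count, which satisfaction item to lead with, what level counts as satisfied or adherent, and what rate is good enough. None of this is fixed, so all of it would be decided with the rates in view. A pass mark cannot be set fairly at that stage, and the natural drift is towards a favourable reading.

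Missing data push the same way. Women who leave the program are the least likely to complete the post-intervention survey, and that survey is the only stated source for attendance and satisfaction.

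**Working it through.** **1. What is fixed and what is open**

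| Endpoint | Fixed | Open in Sections 4 and 18 |
|---|---|---|
| Recruitment | Named as a rate | Denominator, criterion, interval |
| Retention | Named as a rate | Which assessment counts, denominator, criterion, interval |
| Adherence | Two components: sessions and home practice | Rule for either component, handling of non-responders, criterion, interval |
| Satisfaction | Items named | Lead item, cut-off for satisfied, denominator, criterion, interval |

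Section 18 also plans an analysis by high versus low adherence without defining the split.

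**2. The plan's own figures**

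- Section 25, earlier focus-group study: eligible/screened = 18/41 = 43.9% (stated as 44%); recruited/eligible = 15/18 = 83.3% (stated as 83%). Both reproduce. Over screened women the same 15 would be 15/41 = 36.6%, so the denominator matters. Section 25 uses eligible women, but Sections 4 and 18 do not adopt that definition.
- N = 30 (Section 12) agrees with 3 waves of about 10 (Section 6) and exceeds 12. No formula can reproduce it, because the documents give no target rate, error rate, power or interval width.

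**3. Precision**

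Exact (Clopper-Pearson) 95% limits for x of n: lower = Beta quantile(0.025; x, n − x + 1); upper = Beta quantile(0.975; x + 1, n − x).

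| Observed | Rate | Exact 95% interval |
|---|---|---|
| 18/30 | 60% | 40.6% to 77.3% |
| 21/30 | 70% | 50.6% to 85.3% |
| 24/30 | 80% | 61.4% to 92.3% |
| 27/30 | 90% | 73.5% to 97.9% |
| 10/12 | 83% | 51.6% to 97.9% |

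The last row is at the cited minimum of 12. Recruitment has its own denominator. At the earlier 83.3%, enrolling 30 would take 30/(15/18) = 36 eligible women, and 30/36 has an interval of 67.2% to 93.6%.

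**4. Responders versus enrolled (assumed counts)**

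Suppose 24 of 30 answer the post-intervention survey and 22 of them are satisfied. Over responders this is 22/24 = 91.7%. Over all enrolled it is 22/30 = 73.3%. The gap is 18.4 points, from the choice of denominator alone.

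**5. Whether a pre-set rule works at this size**

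For a rule of at least 24/30, P(X ≥ 24) = Σ C(30,k) p^k (1 − p)^(30 − k), for k = 24 to 30. The threshold and the true rates are illustrative, not taken from the documents.

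| True rate p | Probability of meeting the rule |
|---|---|
| 60% | 0.017 |
| 70% | 0.160 |
| 80% | 0.607 |
| 90% | 0.974 |

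A rule set this way separates 60% from 90% well. A program truly at 80% would miss it with probability 1 − 0.607 = 0.393. A lower mark, at least 23/30, would be met with probability 0.044 at 60% and 0.76 at 80%.

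These figures treat the women as independent. Sessions run in groups of about 10, so attendance and satisfaction may cluster by group. The intervals would then be too narrow and the probabilities too optimistic.

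**The case against.** The strongest reply is that this is an exploratory one-arm pilot. Its objective is to evaluate, Section 5 says explore, no hypothesis is stated, and an evaluative aim can be met by reporting rates. That stands in part. A reader might infer that the primary objective cannot be answered at all, and the documents do not support this: the rates can be estimated and described. What is missing is a basis for a conclusion fixed in advance, and the wording in Sections 3 and 5 invites such a conclusion.

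A reader might also infer that the choice among satisfaction items is wide open. It is narrower than that. The Section 6 table lists satisfaction, stress management, and group and instructor environment separately, and Section 4 puts the overall program item first. That item is the obvious lead, although it is not named as such.

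Three further points are fair:

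- Section 25 already shows how the team computes a recruitment rate, so that gap is one of wording.
- A reader can compute an interval once the counts are published, so its absence does less harm than the absence of a criterion or denominator.
- The documents describe no later trial or progression decision, so they give no ground for demanding formal go, amend and stop bands. A stated feasibility criterion is enough.

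**Conclusion.** The concern holds in this form: Sections 4 and 18 allow recruitment, retention, adherence and satisfaction to be estimated, but set no criterion, denominator or interval for any of them. They therefore cannot support a pre-specified conclusion that the program is, or is not, feasible and acceptable.

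The consequence is moderate. At n = 30 the exact 95% interval is roughly 15 to 20 points either side for observed rates of 60% to 80%. The denominator could move satisfaction by about 18 points in the assumed case; the true shift depends on how many women fail to respond, which the documents do not predict.

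A reader might infer that 30 women are too few for a criterion to be useful. The calculations do not bear that out, although a mark set at the hoped-for rate will often be missed by chance. All thresholds and true rates used here are illustrative, and the probabilities assume independence between participants.

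**What to change.** Before wave 1 starts, amend Sections 4 and 18 so that each primary endpoint has one numerator and denominator, an exact 95% confidence interval, and a feasibility criterion chosen and justified by the investigators:

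- **Recruitment:** enrolled over eligible, as Section 25 already computes it.
- **Retention:** one-month assessment completed, over all enrolled.
- **Adherence:** sessions attended, over all enrolled, taken from Zoom attendance where available so that non-responders are counted. Section 19 has the principal investigator present at every session, so a log should be easy to keep. Keep home practice as the second component, with its own definition.
- **Acceptability:** the overall program satisfaction item as lead, with a stated cut-off for satisfied, shown over all enrolled and over responders. Instructor and group items are supportive.

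Add to the sample-size paragraph in Section 18 the precision that 30 women give (24/30: 61% to 92%; 21/30: 51% to 85%). For any threshold chosen, add the probability of meeting it at several true rates, with a note that delivery in groups may weaken the independence assumption.

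The change needs no extra participants or visits, only protocol wording and an attendance log. The cost is that the investigators commit to marks they could miss, including by chance.

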Individuals will receive the 4-week tailored intervention in groups (3 waves of approximately 10 participants each; these may be stacked, overlapping, or following completion of each group, according to the instructor's availability). All weekly sessions will be delivered via Zoom. My team and I have the expertise and are equipped to recruit and implement the telephone-delivered program given our prior virtual studies in Puerto Rico and US Latinxs during the COVID-19 pandemic. Once in the intervention, participants will join one session weekly (on Zoom) and will receive access to online audio files, which are the daily practice exercises to be done at home.

Each session has a duration of 1hr (except the first session which is longer due to introductions and describing the program's logistics and expectations). The sessions follow a brief check-in, lecture on the week's topic, and guided practice. For the audio files, for each exercise, participants will have the opportunity to select a short version of the practice (5-8min) or a longer version (12-16min) according to their daily availability. The following table outlines the 4-week MBSR session topics and daily home-practice exercises.

Session	Topic	Home exercise
Week 1	Orientation; Introduction to stress and its consequences	Awareness of breathing
Week 2	Awareness of sensations	Body Scan
Week 3	Thoughts are not facts	Awareness of thoughts
Week 4	Recap; Mindful eating, mindful walking	Awareness of eating

After completion of the intervention, participants are encouraged to continue doing the mindful daily exercises at home by accessing the audio files. Following the last session, participants will be given access to the online questionnaire for the post-intervention measures, which will include the Contact information form. Research staff will have 10 attempts (via email, text or call) to contact participants and remind them to fill out the questionnaire.

1mo post-intervention, participants will be contacted to complete the third and final assessment, an online questionnaire, which will also include the Contact Information Form. The link to the survey will be

---

**Protocol Title:** Shift-and-persist and cardiometabolic markers among women in Puerto Rico: a pilot of a mindfulness-based trial

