provided and up to 10 reminders (via email, text or call) will be sent out to complete the assessment. The link to this last assessment will be sent out 1-month after completion of the intervention, but at least 3 weeks after the post-intervention assessment.

A weekly reminder will be sent out (the day prior to the session, via text and email) to remind participants to join the weekly Zoom call. Up to 10 reminders (on each occasion, via text, email or call) will be sent out to participants to complete the baseline, post-intervention, and 1mo post-intervention online questionnaire.

All gift cards will be electronic gift cards and the information will be sent out to participants via email or text.

Participants will be notified that all experiences shared during intervention sessions are considered confidential and should not be discussed outside of the group.

The following table shows the different measures being collected at the different time points (also see questionnaire/instruments provided for data collection at baseline, post-intervention, and 1mo post-intervention).

Timepoint	Baseline	Post intervention	1mo post intervention
Socio-demographics			
Age	X		
Gender	X		
Health insurance	X		
Education	X		
Income	X		
Municipality	X		
Food security	X		
SNAP	X		
Marital Status	X		
Perceived income	X		
Employment	X		
Mental health			
Depression (CESD-10)	X	X	X
PTSD (PCL-2)	X	X	X
Anxiety (GAD)	X	X	X
Perceived stress (PSS-4)	NA-included in screening	X	X
Resilience			
SP (Chen et al)	X	X	X
Mindfulness (FFMG-15)	X	X	X
Psychological flexibility (AAQ2)	X	X	X
Health behaviors			

PA (WHI)	X	X	
Perceived sleep qual	X	X	
Diet screener (Mattei et al)	X	X	
Emotional eating (TFEQ R18 V2)	X	X	X
Reward based eating (Reward based eating scale (RED))	X	X	X
Smoking	X	X	
e-cigarettes	X	X	
Clinical characteristics			
Self-reported diagnosis	X		
Medical care for mental health	X		
Medications for mental health	X		
Anthropometrics			
Self-reported blood pressure	X	X	X
Self-reported weight	X	X	X
Self-reported height	x	x	x
Self-reported pulse	x	x	x
Intervention			
Satisfaction		X	
Stress management		X	
Group and instructor environment		x	
Exercise that helped the most		X	X
Exercise most often practiced		X	X
# sessions attended		x	
Frequency of daily practice and duration		X	X
Overall feedback		X	

We have delineated a suicide prevention protocol as explained in section #19 of this document.

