#### **14. Withdrawal of Participants**

Participants can leave a study at any time without penalty.

The person in charge of the research study, [name] [name], or any of the study representatives designated by her can remove a study participant due to lack of commitment to the

---

study, hostility or aggressive behavior towards study staff, study discontinuation, or changes in study protocols.

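### Session attendance, part of the primary adherence endpoint, is collected only by the post-intervention questionnaire, so women who do not answer have no value and adherence is likely to be overstated

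*Combined protocol and SAP*

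**What the plan says.** Section 4 (Primary endpoints) lists adherence with recruitment, retention and satisfaction. It defines adherence in one sentence: "Adherence will be measured by the number of phone sessions attended and the frequency of self-reported completed home practice, both assessed at post-intervention assessments". The next bullet, on satisfaction, says that those ratings are also collected by survey at the same assessment.

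Section 5 gives the mode of collection: "All study measures at all time points will be done online through questionnaires to be filled out by participants". In the Section 6 schedule, the row for number of "sessions attended" is marked at post-intervention only. The row for frequency and duration of home practice is marked at post-intervention and again at 1 month.

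On timing, Section 6 says: "Following the last session, participants will be given access to the online questionnaire for the post-intervention measures". Staff may make up to 10 contact attempts to obtain it.

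Section 18 says: "Recruitment, adherence, retention, and satisfaction will be calculated for the total sample". It also plans an exploratory comparison of women with high and low adherence. It gives no rule for a woman without a post-intervention questionnaire.

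**The concern.** Feasibility and acceptability are the primary objective, and attendance is the most direct evidence of whether young women will take part in a 4-session program. As written, that evidence exists only for women who complete a questionnaire after the program has ended. A woman who stops attending but still answers is counted. A woman who stops attending and does not answer is not.

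Three features of the plan make non-response likely to go with low attendance:

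- The questionnaire is released only after the last session, when a woman who left early may already be out of touch.
- Under Section 14 the study lead or a delegate "can remove a study participant due to lack of commitment to the" study, so the least engaged women may be gone before the questionnaire is issued.
- Under Section 17 the largest gift card ($50 of $100) requires both the program and the second assessment, so a woman who dropped the program may have less reason to answer.

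Retention, reported beside adherence, would show how many women are missing but not how many sessions they attended. The exploratory comparison by adherence could not classify these women on attendance either.

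**Working it through.** **Source of the measure.** Section 4 places the assessment of attendance at the post-intervention assessment. Section 5 says the assessments are participant-completed questionnaires. The Section 6 schedule marks attendance at that time point and no other, so the 1-month questionnaire cannot recover a missing value. No section names a roster, a Zoom log or a staff count as the data source. The three places agree.

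**Size.** The plan states no expected attendance, adherence target or non-response rate, so there is no figure of its own to reproduce.

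Inputs from the documents:
- N = 30 women (Section 12)
- 4 sessions (Section 5)

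Assumed inputs:
- k, number of women not answering: 2, 3, 6 or 9
- responder mean: 3.5 of 4 sessions
- m, non-responder mean: 0 to 2 sessions

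The value k = 2 scales the nearest figure in the documents. Section 25 reports that 1 of 15 recruited women did not join her focus group; at that rate, 30 × 1/15 = 2. That was a single call, a lighter commitment than this program, and it concerns attending a call rather than answering a questionnaire.

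Formulas:
- Mean over all enrolled = ((30 − k) × 3.5 + k × m) / 30
- Overstatement = 3.5 − that mean = (k/30) × (3.5 − m)

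| k (share) | True mean, m = 0 | True mean, m = 1 | True mean, m = 2 | Overstatement (m = 2 to m = 0) |
|---|---|---|---|---|
| 2 (6.7%) | 3.27 | 3.33 | 3.40 | 0.10 to 0.23 |
| 3 (10%) | 3.15 | 3.25 | 3.35 | 0.15 to 0.35 |
| 6 (20%) | 2.80 | 3.00 | 3.20 | 0.30 to 0.70 |
| 9 (30%) | 2.45 | 2.75 | 3.05 | 0.45 to 1.05 |

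With a responder mean of 3.0 instead, the overstatement runs from (2/30) × (3.0 − 2) = 0.07 to (9/30) × (3.0 − 0) = 0.90 sessions. If m equals the responder mean, it is 0.

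**Can an analysis rule repair it?** Take k = 6 and m = 1. The true mean is (24 × 3.5 + 6 × 1)/30 = 90/30 = 3.00.
- Responders only: 3.50, an error of +0.50.
- Non-responders coded 0: 24 × 3.5/30 = 2.80, an error of −0.20.

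Neither rule recovers 3.00.

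**As a proportion.** Suppose good attendance means at least 3 of 4 sessions (an assumed cut-off), 6 women do not answer, and 22 of the 24 responders meet it. The questionnaire gives 22/24 = 91.7%. For all 30, the data allow anything from 22/30 = 73.3% to 28/30 = 93.3%. The reported figure sits near the top of that range.

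**The case against.** The strongest reply is that an undescribed source is not a lost one. In Section 4, self-report grammatically qualifies home practice and not attendance. The Section 5 statement is not literally true of everything: baseline PSS-4 comes from the phone screening, and recruitment and retention are necessarily staff counts. The principal investigator is present at every session (Section 19). Paying for program completion and removing women for lack of commitment both seem to require knowing who came. Staff may therefore hold attendance information.

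Part of this stands: operational records may exist. But the PSS-4 exception is marked as such in the schedule, the investigator's presence is for fidelity, and no section makes such a record the source of the endpoint. If a log is already intended, one sentence settles the matter.

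The direction and size can also be questioned. All women receive the questionnaire at the same point, up to 10 contacts are made, women who do not finish are still paid for completed visits, and Section 6 reports good response rates, without a figure, in the investigator's other online surveys. These points stand as limits on how many women will be missing; they supply no value for a woman who stays silent. The upward direction is an inference, and the larger figures in the table have no support in the documents beyond the stated assumptions.

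Finally, the plan sets no adherence threshold, so no formal decision turns on a shift of this size. In the comparison by adherence, a non-responder also lacks post-intervention outcomes and could contribute follow-up data only at 1 month. Both points reduce the consequence, but the estimate itself is what a feasibility pilot is run to obtain.

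**Conclusion.** The concern holds. Followed as written, the plan leaves part of a primary feasibility measure missing for every woman who does not return the post-intervention questionnaire, while promising that measure for all enrolled women. Upward bias is likely but not certain: it requires non-responders to have attended less than responders.

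The size depends on response, which the documents do not predict. At the one nearby rate they offer (2 of 30), it is about 0.1 to 0.2 of 4 sessions, which is modest. With 6 to 9 women missing it would be 0.30 to 1.05 sessions, enough to change how feasible the program looks. This should be fixed before the first wave begins, because attendance not noted at the time may be impossible to reconstruct. It does not threaten the viability of the trial.

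**What to change.** - In Sections 4 and 6, state that attendance of every enrolled woman is recorded at each Zoom session, on a sheet kept by the principal investigator or from the Zoom log.
- Define session adherence as the number of sessions attended (0 to 4), with all enrolled women as denominator and a missed session counted as 0.
- Use this recorded count in the exploratory adherence comparison in Section 18.
- Keep self-report for home practice only, and report it with the number of women who answered.
- Editorial: Section 4 refers to phone sessions, whereas Section 6 says "All weekly sessions will be delivered via Zoom". Align the wording.

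The cost is a short attendance sheet for 4 sessions × 3 waves = 12 sessions, kept by someone already present, with no added burden on participants. Reported adherence may look less favourable. Home practice and post-intervention outcomes of non-responders will still be missing.
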